### 3.7 Safety Endpoints

This study will assess safety and tolerability in individuals at risk for dominantly inherited AD. Safety endpoints used will be the incidence and severity of treatment-emergent adverse events (TEAEs), serious adverse events (SAEs) and treatment discontinuations. Analysis will be on an intent-to-treat basis. Clinical laboratory evaluations, vital signs, and 12-lead ECGs will also be measured throughout the study.

Amyloid-related imaging abnormalities (ARIA) are a safety endpoint in studies of DAT. Based on the assigned study drug arm, this study may include MRI scans every few months to assess for ARIA changes. ARIA can occur as either cerebral edema (ARIA-E) or as hemorrhages (ARIA-H), typically microhemorrhages, but larger hemorrhages and frank infarction have also been reported (Sperling, Salloway et al. 2012). MRI scans will be analyzed for ARIA changes at the Mayo Clinic Aging and Dementia Imaging Research (Mayo-ADIR). The number of microhemorrhages (ARIA-H, including both hemorrhages and hemosiderin deposits) and size of

areas of edema (ARIA-E) will be monitored at entry and throughout the trial. Incidence of ARIA and comparison to placebo will be made.

A report of new ARIA changes in a subject will trigger a review by the DIAN-TU Medical Director or designee, Project Arm Leader (PAL), and site principal investigator. This review will include contact with the subject or caregiver to assess for any symptoms associated with the changes and discussion with the central readers. The PAL, as a site independent neurologist, will help ensure consistency of decisions within a study drug arm across sites during the study. See each drug-specific appendix for drug-specific ARIA algorithms. The DIAN-TU Medical Director will ensure consistency across study drug arms and will have final decision-making authority on changes in dosing of study drug or safety monitoring; this decision should be received by the site within 7 days of the report of the new ARIA changes, but no later than the day prior to the planned administration of the next dose of medication. A similar process will be followed if a follow-up MRI shows worsening of a previously reported ARIA.

Additional assessments based on drug-specific safety concerns are detailed in each drug-specific appendix (Appendices 3 and 4).

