### 6.3.7 Early Termination/Post-treatment Follow-up

If a subject withdraws, is terminated from the study prior to completion of the double-blind treatment period, or is in a study drug arm that is stopped prior to the end of the double-blind treatment period, every effort should be made to schedule an early termination visit. PET imaging studies may be omitted if early termination occurs less than 6 months after the previous PET imaging or if precluded by local regulations/dosimetry limits. Other procedures may also be eliminated on a case-by-case basis, as determined by the sponsor or if not required based on the study drug arm procedures or study period.

Any subject that meets study drug discontinuation criteria per section 4.4.1 (excluding subjects who are known mutation negative) will be encouraged to continue participation in any of the scheduled clinical, cognitive, and/or biomarker assessments that are able to be performed even though dosing has concluded. The determination of which assessments to be attempted/completed will be decided with the site principal investigator and sponsor based on the subject's capabilities, the benefit to the study, and the risk associated with continued participation at the time of study drug discontinuation. The level of continued participation may change if/as the subject's status changes.

*Location:* DIAN-TU site or at the subject's home or other trial-identified location with the trial-designated home health nurse

*Time/Timing:* The early termination visit may occur at any time during the study. Approximately a 3-4 day visit. For subjects who live near the study site, these visit procedures may be scheduled over a longer time period of up to 2 weeks.

*Procedures:* **See each drug-specific appendix for the specific assessments that are required at each visit.** Procedures may include any of the following:

- Medical/treatment history, including:
  - Concomitant medications

- Assessment /recording of adverse events
  - Laboratory sample collection (baseline drug-specific tests, stored plasma and/or serum, and clinical safety assessment)
  - Administration of C-SSRS
  - Vital signs (blood pressure, heart rate, respiratory rate, body temperature, weight and height)
  - Physical and neurological examinations
  - Clinical assessments:
    - CDR including calculation of CDR-SB
    - NPI-Q
    - GDS
    - FAS
    - MMSE
    - Assessment of clinical diagnosis and clinician judgment of symptoms.

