#### **7.4 Adverse Event Collection Period**

All AEs reported from the time that informed consent is obtained until 30 days following the last dose of study drug [REDACTED] will be collected, whether elicited or spontaneously reported by the subject. Adverse events should be collected at End of Study and Early Termination visits even if these visits occur more than 30 days after last dose of study drug. Serious adverse events considered related to study drug or procedures should be reported even if they occur more than 30 days after the last dose of study drug.

At every study visit, subjects will be asked a standard question to elicit any medically related changes in their well-being. They will also be asked if they have been hospitalized, had any accidents, used any new medications, or changed concomitant medication regimens (both prescription and over-the-counter medications).

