### **NN19866 Magnetic Resonance Imaging**

The multiple ascending dose (MAD) study NN19866 was prematurely terminated (after patients in the 200-mg group had received 2 to 5 doses) due to ARIA-E seen after 2 to 4 doses of gantenerumab 200 mg. Notably, the findings, best seen on the Fluid Attenuated Inversion Recovery (FLAIR) sequences, were only reported in carriers of *APOE-4* and seemed more prominent in patients who were homozygous for *APOE-4* (E4/E4). Concomitant ARIA-H microbleeds were only observed in the two carrier patients homozygous for *APOE4* (E4/E4). No patient required treatment and the ARIA-E findings spontaneously resolved 1-4 months after discontinuation of gantenerumab.

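### For subjects followed off drug, section 7.4 ties AE collection to last dose plus 30 days, which conflicts with 7.5 and 7.6 and does not fit the intent-to-treat SAE endpoint in 3.7

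*Protocol*

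**What the plan says.** **Collection window.** Section 7.4 collects "All AEs reported from the time that informed consent is obtained until 30 days following the last dose of study drug". A redaction follows these words in the same sentence. Two extensions come next. The first is "Adverse events should be collected at End of Study and Early Termination visits even if these visits occur more than 30 days". The second is "Serious adverse events considered related to study drug or procedures should be reported even if they occur more than 30 days after the last dose". The section also says: "At every study visit, subjects will be asked a standard question to elicit any medically related changes in their well-being", and adds a question on hospitalisation.

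**Recording and reporting.** Section 7.5 has AEs monitored throughout the study and every AE that is reported or observed entered in the eCRF. Section 7.6 requires any AE that the investigator considers serious to be reported within 24 hours of the site learning of it. Neither section has a time limit after the last dose or a causality filter.

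**Follow-up off drug.** Under 6.3.7, subjects who meet drug discontinuation criteria (other than known mutation negatives) "will be encouraged to continue participation in any of the scheduled clinical, cognitive, and/or biomarker assessments". The site and sponsor decide which assessments continue. Section 4.4.1 says much the same. In Appendix 3, section 1.14, Tables 3 and 4 foresee dosing being discontinued for ARIA-H while other assessments and visits go on. The visit schedule runs to week 364.

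**Analysis.** Section 3.7 lists treatment-emergent AEs, SAEs and treatment discontinuations as safety endpoints and states: "Analysis will be on an intent-to-treat basis". Section 8.2 lists serious AEs and AEs resulting in death, both limited to treatment-emergent events.

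**The concern.** A comparison of SAEs by randomised group needs events to be collected the same way in every group, whether or not drug was stopped. Section 7.4 does not secure that. It makes general collection depend on the date of the last dose, and late SAE collection depend on an investigator's judgment of relatedness. Both can be influenced by treatment.

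The instruction to sites is also inconsistent. One site may stop entering unrelated SAEs at day 30 under 7.4, while another goes on entering them under 7.5 and 7.6. With 52 carriers in each active group and 34 pooled placebo carriers, one SAE more or less moves a group's percentage visibly. The DSMB's quarterly SAE review in 7.9 draws on the same data.

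A statistical analysis plan can choose the analysis period. It cannot recover events that sites were told they need not collect.

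**Working it through.** **1. Do the extensions in 7.4 close the gap?** Take a subject who stops drug at year 2 and attends visits to year 5.

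| Event more than 30 days after last dose | 7.4 | 7.5 and 7.6 |
|---|---|---|
| SAE judged related | reported, no time limit | reported |
| SAE judged unrelated, including a fatal one | only if picked up at an End of Study or Early Termination visit | recorded and reported |
| Non-serious AE | only if picked up at those visits | recorded |

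The follow-up visits do not help much, because they are timed from the last dose and not from the last contact: 4-12 weeks in section 6.3.5, 12 weeks for gantenerumab (Appendix 3, 3.3.15) and 4-8 weeks for solanezumab (Appendix 4, 3.3.16). The Early Termination visit is likewise prompted by stopping early. The related-SAE sentence would be unnecessary if all SAEs after day 30 were already inside the rule. So 7.4, read alone, leaves out unrelated SAEs in the off-drug years, and the second and third rows of the table conflict.

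**2. Does this reach the planned analysis?** Section 3.7 names SAEs apart from treatment-emergent AEs and without a treatment-emergent limit, under an intent-to-treat statement. That endpoint is affected. Deaths are affected only through it, because 7.1.2 makes a death an SAE. The analyses in 8.2 are treatment-emergent and are compatible with a last dose plus 30 days window.

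**3. Size, for illustration.** The plan gives no figure to reproduce. From the documents: 52 carriers per active group and a mean duration of 5.3 years. Assumed: a share p stops at year 2, 80% of these stay in follow-up, and 7.4 is applied as a hard stop.

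- Total person-time: 52 × 5.3 = 275.6 person-years.
- Exposed time per retained stopper: 5.3 − 2 − 30/365.25 = 3.22 years.
- Exposed person-time: 52 × p × 0.8 × 3.22.

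| p | Person-years | Share of 275.6 |
|---|---|---|
| 5% | 6.7 | 2.4% |
| 10% | 13.4 | 4.9% |
| 20% | 26.8 | 9.7% |

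**4. A second set of assumptions.** Suppose the protocol's 5% annual attrition were all drug stopping, at a constant hazard λ = −ln(0.95) = 0.0513 per year, with every stopper followed to T = 64 months (5.33 years). With w = 30/365.25 = 0.082 years, collected time per subject is w + [1 − exp(−λ(T − w))]/λ = 4.69 years. The uncollected share is 1 − 4.69/5.33 = 12.1%, or about 34 of 277 person-years for 52 subjects. This is the upper bound under that rate, since attrition normally includes subjects lost to follow-up altogether.

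**5. Weight of one event.** One SAE is 1/52 = 1.9 percentage points in an active group and 1/34 = 2.9 points in the pooled placebo carriers.

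**The case against.** The strongest reply is that recording does not stop. Sections 7.5 and 7.6 require it, each study visit includes the well-being and hospitalisation question, and the gantenerumab schedule marks AE assessment at each post-baseline dosing and annual visit. This stands as far as it goes: it makes the defect a conflict between sections rather than a proven loss of data. It does not remove the conflict, because 7.4 is the section that defines the collection period, and 6.3.7 does not name AE assessment among the procedures that subjects are encouraged to continue.

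A reader might infer four stronger things that the documents do not support:

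- **That an intent-to-treat death comparison is cut short.** Section 3.7 does not name death, and 8.2 restricts deaths to treatment-emergent events. The intent-to-treat wording in 3.7 may also mean only analysis by randomised group.
- **That the active arm is made to look safer.** No difference in stopping is shown. Appendix 3, section 1.5, reports nearly identical attrition on placebo, 105 mg and 225 mg in an earlier gantenerumab trial. Appendix 4, section 1.6, gives ARIA-E in 0.6% versus 0.3% and infusion site reactions in 2.1% versus 2.0%. A dose hold with restart is not a last dose. Titration here goes to 1200 mg, so a difference remains possible, but it is not demonstrated.
- **That the protocol's own data prove 30 days too short.** The report that "the ARIA-E findings spontaneously resolved 1-4 months after discontinuation of gantenerumab" concerns resolution of findings already detected, and 7.5 follows AEs to resolution. Persistent plaque binding in mice is not safety-event data.
- **That the visible wording of 7.4 is complete.** The redaction may hide a qualifier. The related-SAE sentence that follows is still legible and still implies a limit.

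**Conclusion.** The point holds as an unresolved conflict. For subjects followed off drug, 7.4 makes collection depend on drug stopping and judged relatedness, while 7.5 and 7.6 do not, and the 7.4 rule does not fit the SAE endpoint in 3.7. What is at risk is uneven capture of unrelated SAEs, fatal or not, and of non-serious AEs after day 30. Related SAEs are not lost.

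The exposed share of active-arm person-time is about 5-10% if 10-20% stop at year 2 and 80% of them stay in follow-up, and 12.1% under the second set of assumptions. These shares rest on assumed stopping and retention and on a hard reading of 7.4. They measure exposed time, not bias, and the direction of any bias cannot be stated. The change should be made because it is cheap and removes an avoidable dependence, not because a distortion has been shown.

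**What to change.** Reconcile 7.4 with 7.5, 7.6 and 6.3.7. State that for subjects who stop study drug but remain in any follow-up, all SAEs, including deaths, are collected regardless of causality through the last study contact. Name AE assessment in 6.3.7 among the procedures that continue. Say in 7.4 whether non-serious AEs keep the 30-day limit.

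Report SAEs by randomised group over all follow-up, with the on-treatment plus 30 days analysis beside it, and make clear which of the two the intent-to-treat statement in 3.7 refers to.

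The cost is a wording change and extra SAE entry for background and disease-related events. The visits and the standard question already exist.

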#### **7.5 Adverse Event Reporting**

The investigator will monitor each subject for clinical and laboratory evidence of AEs on a routine basis throughout the study. Conditions present at baseline will be documented. Deterioration or worsening of conditions present at baseline should be reported as an AE. All AEs reported or observed during the study will be recorded in the AE eCRF. Information to be collected includes the type of event, date of onset, investigator-specified assessment of severity and relationship to study drug, date of resolution of the event, and seriousness. Treatments for AEs will be recorded on the concomitant medication eCRF. AEs resulting from concurrent illnesses, reactions to concurrent illnesses, reactions to concurrent medications, or progression of disease states must also be reported. All AEs, whether serious or non-serious, should be followed to resolution or until the AE is determined by the investigator not to be clinically significant or to be chronic or stable. Medical Dictionary for Regulatory Activities (MedDRA®) will be used to code all AEs.

#### **7.6 Serious Adverse Event Reporting**

The principal investigator must report to [REDACTED] Safety (formerly known as [REDACTED]) any AE considered serious by the investigator, or which meets any of the specified criteria in section 7.1.2. Refer to each drug-specific appendix for drug-specific AE and SAE reporting. The initial report must be submitted within 24 hours from the time site personnel first learn about the event by entry in inform (EDC); in cases where a back-up submission method is needed the site must submit SAE documentation to the project mailbox: [REDACTED]

Contact information for █████ Safety:

█████ **SAFETY:**

Toll-free for US sites:

Phone: █████

Fax: █████

For all sites/international:

█████ or

█████ (alternative number)

Additional contact information is detailed in the *Global Manual of Operations*.

The reporting should include completion of the eCRF Adverse Event Form with Serious event indicated as Yes, and verification of current data entry in the eCRFs or de-identified source documents for the demographics page(s), medical history page(s), AE page(s) and concomitant medication page(s). If the subject is hospitalized because of or during the course of an SAE, then a copy of the hospital discharge summary should be faxed to █████ Safety as soon as it becomes available. Withdrawal from the study and all therapeutic measures will be at the discretion of the investigator unless the event meets a protocol-specified discontinuation criterion. All SAEs will be followed until satisfactory resolution or until the investigator deems the event to be chronic or the subject to be stable.

The sponsor or its designee will be responsible for reporting SAEs to FDA, European Medicines Agency (EMA) and other relevant regulatory authorities accordingly to local regulatory requirements. Sites are responsible for reporting to their local ethics committees /IRBs per their reporting requirements and/or local laws.

## 7.7 Pregnancy Reporting

Cases of pregnancy that occur during maternal or paternal exposures to study drug or within 16 weeks following last dose of study drug should be reported. Data on fetal outcome and breast-feeding are collected for regulatory reporting and drug safety evaluation. Sites should report pregnancies to █████ Safety in the same manner and timing as for Serious Adverse Events specified in section 7.6.

## 7.8 Adverse Events of Special Interest

Refer to the drug-specific appendices for drug-specific reporting for adverse events of special interest (AESI). Sites should report an AESI to █████ Safety in the same manner and timing as for Serious Adverse Events specified in section 7.6.

## 7.9 Data Safety Monitoring Board (DSMB)

Unblinded data from study drug arms on safety-related endpoints (clinical laboratory test results, ECGs, MRI findings, cognitive and clinical endpoint results) and SAEs will be reviewed quarterly by the DSMB. Complete details are available in the DSMB charter.

## 8 STATISTICAL PLAN

[REDACTED] All statistical analyses described are related to the study drug arms that are included in this protocol.

A detailed statistical analysis plan will be used for interim and final efficacy analyses and for the biomarker interim analyses.

### 8.1 Descriptive Statistics

Descriptive statistics will be provided for safety and efficacy variables at each time point collected by treatment groups and across combined placebo groups. Continuous variables (e.g., biomarker values) will be summarized using the number of observations, mean, standard deviation (SD), minimum, lower quartile, median, upper quartile, and the maximum. These statistics will be provided by PROC UNIVARIATE/SAS (SAS Institute Inc. 2009). Categorical variables (e.g., presence of absence of an *APOE ε4* allele) will be summarized using the number and percentage in each category.

### 8.2 Safety Analysis

Safety analysis will include all subjects who consent to participate and are randomized to receive any study-related drugs or placebo and will be reported to an independent Data Safety Monitoring Board (DSMB) for regular reviews. The following are major safety endpoints that will be analyzed: treatment-emergent adverse events (AE), serious treatment-emergent AEs, serious drug-related treatment-emergent AEs, treatment-emergent AEs that lead to discontinuation of the study, treatment-emergent AEs resulting in death, safety MRIs, laboratory parameters, vital signs and physical examinations. Adverse event reporting will include the severity, onset, duration, relief measures, outcome, and relationship to study drug. Adverse events will be classified using MedDRA preferred terms. Adverse events noted on MRI scans, including ARIA, will be analyzed as will adverse events noted as significant changes or new abnormalities in vital signs, clinical laboratory test values or ECGs.

### 8.3 Biomarker Endpoint Statistical Analysis, Power and Sample Size Justification

Each drug that enters the DIAN-TU platform trial will have biomarker defined interim analyses. The goal of the interim analyses is to stop or adjust a treatment that is not demonstrating

sufficient efficacy on the target biomarker. Each study drug arm will have a target biomarker, a target biomarker analysis, and a remediation plan should the biomarker analysis demonstrate lack of success. The remediation plan will include dose-adjustment strategies, if appropriate, to maximize the efficacy, if the tolerability and safety profile is acceptable. If no adjustments are possible, then failing the biomarker interim will lead to stopping the regimen for futility. Each drug-specific appendix will detail the biomarker interim analysis. The biomarker interim analyses will only be used for dose-adjustment, remediation, or stopping a study drug arm for futility and will not be used for any conclusion of success or efficacy on the primary cognitive endpoint.

Interim biomarker analyses will be conducted for each study drug arm to assess whether the active study drug is engaging its biological target. The timing of the interim biomarker analyses may vary for each study drug arm. At each interim, an analysis will be conducted for the biomarker endpoints, comparing the active drug to its own (direct) placebo group or to a pooled placebo group (mutation positive placebos). Pre-specified definitions for early termination for futility will be drug-specific and based on collection of appropriate biomarker assessments following sufficient drug exposure. Details about the interim biomarker analyses are described in each drug-specific appendix.

## **8.4 Cognitive Endpoint Statistical Analysis, Power and Sample Size Justification**

### **8.4.1 Cognitive Analysis Populations and Primary Efficacy Analysis**

The modified intent-to-treat (mITT) population is defined as all subjects who will be randomized, treated, and assessed for their primary cognitive outcomes at least once after the baseline assessment.

All efficacy analyses will be conducted on the mITT population and the eligible DIAN-OBS subjects.

The primary efficacy outcome (DIAN-MCE) is defined in section 3.5. The primary efficacy hypothesis will be tested by comparing the relative rate of cognitive decline between the active drug and the mutation positive placebos and the eligible DIAN-OBS subjects using the MDPM developed by the DIAN-TU. The MDPM includes 2 subject-level random effects to account for the between-subject variability and a model of the mean rate of decline as a function of expected years from symptom onset (EYO) to estimate a proportional slowing of decline of the primary endpoint in active drug compared with the mutation positive placebos and the eligible DIAN-OBS subjects. This model was developed using Data Freeze 13 from the DIAN-OBS study. To test the hypothesis of a disease progression benefit we calculate the posterior probability of superiority in cognitive slowing and if it is above a pre-specified threshold (which controls the experiment wise type I error at 2.5%) then a claim of cognitive slowing will be made. The pre-specified threshold may vary from study drug to study drug depending on the drug-specific sample size or the interim analysis plan. All these analyses will be implemented using SAS or validated MDPM software.

Final analysis will be pre-specified in the SAP and drug-specific SAP appendices.

